8.7. Time-Based Analyses

Mean changes from baseline in the co-primary endpoints will be described in terms of time savings. The mean change from baseline at Week 76 in the active arm will be mapped back to the time point at which the mean change in the placebo arm was equal to the active arm change at Week 76. A cubic spline interpolation will be used for precise time mapping between visits. Similar mappings will be done for the mean changes \pm the SE of the mean changes. If a time mapping is outside the range spanned by the reference trajectory (e.g., mapping standard errors near the beginning or end of follow-up), time will be mapped off the range spanned by the reference trajectory via the line connecting the first visit for change from baseline (0, 0) for change from baseline measures and last visit measures. This time component test will be done based on all participants and for the mild and moderate subgroups.

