Descriptive summary tables for efficacy endpoints will generally include: number of participants with data, mean, standard deviation, median, 25% percentile, 50% percentile, 75% percentile, minimum and maximum. Inferential efficacy summary tables will include within group mean changes from baseline along with the difference between groups in mean change and the associated standard errors and p values.

Baseline is defined as the most recent non-missing measurement collected prior to the first dose.

[figure not shown]
2. Overall Study Design and Plan

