2.2. Sample Size and Power

The sample size for this study was originally determined as follows.

Planned enrollment was approximately 1083 participants with mild-to-moderate AD. The sample size was determined by a power analysis of ADAS-Cog using data from a similar population over 76 weeks. This analysis determined that the comparison between an active arm and placebo requires group sizes of 289 to provide 90% power to detect a 45% difference from placebo at 76 weeks, based on the use of a two-sided test at the alpha = 0.05 significance level. The power calculation assumes a true mean change from baseline for placebo of 6.0 points and a standard deviation of 10.0 points. Assuming a drop-out of 20%, each treatment group should enroll approximately 361 participants.

Learnings from analyses of the sister study, and results from other development programs in AD led to change in the primary analysis population for this study to include in the primary analysis only those participants with >= 44 pg/ml P-tau181 at baseline, or other confirmation of amyloid pathology (e.g., amyloid PET). Based on results of study PTI-125-07, it is anticipated that the reduction in sample size will be offset by an increase in treatment effect such that the study will have at least as much power as originally planned.

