2.4. Treatments Administered

Participants were randomized in a 1:1:1 ratio to:

- simufilam 50 mg tablets BID, or
- simufilam 100 mg tablets BID, or
- placebo tablets BID.

The randomization was stratified by baseline low or high MMSE score (16-20 vs. 21-27).

[figure not shown]

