4.2. Introduction

Data processing, tabulation of descriptive statistics, calculation of inferential statistics, and

Version 1.0 | 28-Feb-2025 Page 17 of 56

graphical representations will use SAS (release 9.4 or higher). If the use of other software is required, the final clinical study report will specify the software that was used.

In general, summaries will be provided by study treatment group, unless otherwise noted. The column headings for the summaries will include the randomized treatment groups (Placebo BID, Simufilam 50 mg BID, Simufilam 100 mg BID), unless otherwise noted.

Continuous (quantitative) variable summaries will include the number of participants with non-missing values (n), mean, 2-sided 95% confidence interval (CI), standard deviation (SD) and/or standard error (SE) if applicable, median, and minimum and maximum values.

Categorical (qualitative) variable summaries will include the frequency and percentage of participants who are in the category for each possible value. In general, the denominator for the percentage calculation will be based upon the total number of participants in the study population for the treatment groups (or cohorts) unless otherwise specified.

The minimum and maximum will be reported with the same degree of precision (i.e., the same number of decimal places) as the observed data. Measures of location (mean and median) and bounds of CIs will be reported to 1 degree of precision more than the observed data and measures of spread (SD and SE) will be reported to 2 degrees of precision more than the observed data. Percentages will be presented to 1 decimal place.

Statistical testing and inference methods for safety and efficacy analyses are described below. Efficacy results will be considered statistically significant after consideration of the strategy for controlling the Type 1 error as described in Section 6.1.2 of this SAP. Nominal p-values may be computed for other efficacy analyses as a measure of the association between the endpoint and the treatment effect rather than formal tests of hypotheses. Unless otherwise stated, all statistical tests will be conducted at the alpha = 0.05 (two-sided) level, and a difference resulting in a p- value of ≤ 0.05 will be considered statistically significant. Corresponding 95% two-sided CIs will be presented for statistical tests.

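### The time-savings error bars in SAP 8.7 treat the estimated placebo curve as known, so they are too narrow if read as uncertainty in weeks saved

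*SAP*

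**What the plan says.** SAP 8.7 converts each co-primary result to a time scale: "The mean change from baseline at Week 76 in the active arm will be mapped back to the time point" at which the placebo arm had changed by the same amount. A cubic spline joins the placebo visit means. Beyond the range of the placebo curve, a straight line from the origin to the last visit is used instead.

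For uncertainty, the section says "Similar mappings will be done for the mean changes" plus or minus their SE. It does not name the arm whose SE is meant. It gives no variance, interval or resampling step for the weeks saved. It ends: "This time component test will be done based on all participants and for the mild and moderate subgroups". No test statistic or rejection rule is defined. SAP 8.5 and 8.6, by contrast, name the CMH test.

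Elsewhere the SAP covers the score scale only. SAP 1 (Overview) says "Inferential efficacy summary tables will include within group mean changes from baseline along with the difference between groups in mean change", with SEs and p-values. SAP 4.2 adds: "Corresponding 95% two-sided CIs will be presented for statistical tests".

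The tables and figures carrying the time-component label are T14.2.1.2.20 and F14.2.1.2.20 for ADAS-Cog12, and T14.2.2.2.20 and F14.2.2.2.20 for ADCS-ADL.

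**The concern.** Time saved depends on two estimates: the active mean at Week 76 and the placebo curve it is read against. SAP 2.4 says "Participants were randomized in a 1:1:1 ratio to" the three arms, so the placebo means should be about as uncertain as the active mean. The planned bars move only the active mean and hold the placebo curve still. They show the active mean's uncertainty on a time axis, not the uncertainty of the time saved.

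Weeks saved is an easily quoted result, and calling the analysis a test invites readers to judge it by whether the bar reaches zero weeks saved. What is at stake is how those displays are read.

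**Working it through.** **Inputs.** SAP 2.2: "The power calculation assumes a true mean change from baseline for placebo of 6.0 points and a standard deviation of 10.0 points"; 289 per group, 90% power, a 45% difference, two-sided alpha 0.05; "Assuming a drop-out of 20%, each treatment group should enroll approximately 361 participants". Assumptions not in the documents: the shape of the placebo decline, the SDs before Week 76, and how many participants reach Week 76.

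**The plan's own figure.** The target difference is 0.45 × 6.0 = 2.7 points. n = 2 × (1.960 + 1.282)² × 10² / 2.7² gives 289 per group. Then 289/0.80 = 361.25, in line with the stated 361, and 3 × 361 = 1,083. The planning figures reproduce.

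**Formula.** Mapped time t solves P(t) = A, where A is the active Week 76 mean and P is the placebo curve. With independent arms, Var(t) = [Var(A) + Var(P(t))] / slope². The planned bar keeps only Var(A). With v = Var(P(t))/Var(A), the shortfall is 1 − 1/√(1 + v).

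**Near no effect (t = 76).** All comparisons are 1 SE against 1 SE.
- Equal arm SEs: v = 1, shortfall = 1 − 1/√2 = 29.3%. This does not depend on n, the SD or the path of SDs over time.
- Placebo variance 0.8 to 1.25 times the active variance: 25.5% to 33.3%.
- Correlation ρ between arm means, equal SEs: shortfall = 1 − 1/√(2(1 − ρ)). That is 25% at ρ = 0.1 and 21% at ρ = 0.2. Positive ρ can arise because SAP 8.1 fits pooled site and SAP 6.1.6 merges small sites, so site sizes will be uneven. Illustrative uneven layouts with equally weighted sites gave ρ of 0.13 to 0.17 and shortfalls of about 22–27%; arm variances need not be equal in such layouts, so these do not follow the formula exactly. With observed-margin weights ρ was near 0 and 29% stands. The SAP does not state the weighting.
- In weeks, assuming linear decline: arm SE = 10/√289 = 0.588 points, slope = 6/76 = 0.0789 points per week, bar = 7.45 weeks. With both arms, 7.45 × √2 = 10.54 weeks.
- A bar of 1/√2 of the correct SE covers about 52% rather than 68%. It would therefore exclude zero weeks saved about 48% of the time under no effect, against 32% for a correct 1-SE bar. Simulation with the spline and the extrapolation line gave shortfalls of 27–29% and coverage of 51–54%.

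**At 45% slowing, linear decline.** Mapped time = 0.55 × 76 = 41.8 weeks. Here v = s × r. The factor s is 0.55² = 0.3025 if SD is proportional to time, 0.55 if proportional to its square root, and 1 if constant. The factor r is n at Week 76 divided by n near Week 42.

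| r | s = 0.3025 | s = 0.55 | s = 1 |
|---|---|---|---|
| 1.0 | 12.4% | 19.7% | 29.3% |
| 0.8 (289/361, all drop-out after Week 42) | 10.3% | 16.7% | 25.5% |
| 0.5 (heavy loss after early termination) | 6.8% | 11.4% | 18.4% |

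With r = 1 and a curved decline 6 × (t/76)^p, p = 0.67 maps to Week 31.1 and gives 7.5–29.3%; p = 1.5 maps to Week 51.0 and gives 17.0–29.3%. The range of roughly 7–29% varies drop-out and curvature one at a time; stacking unfavourable choices would lower the bottom further. Allowing for MMRM borrowing across visits (assumed correlation 0.8 or 0.9 per 12 weeks) gives 11.3–27.9% with 361 falling to 289, and 9.3–25.0% with 361 falling to 180.

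**The kink at Week 76.** With p = 1.5 the spline side has slope 1.5 × 0.0789 = 0.1184, while the extrapolation line has 0.0789. The both-arm SE on the score scale is 0.588 × √2 = 0.832 points. A delta-method SE is then 0.832/0.1184 = 7.0 weeks on one side and 0.832/0.0789 = 10.5 on the other.

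**The case against.** Section 8.7 says it will describe changes as time savings. It defines the bars exactly as what they are and never calls them a confidence interval. Between-arm differences with SEs and CIs are reported on the score scale, and no decision uses the bars. This is fair, and it limits the importance of the point. But nothing in the SAP gives a both-arm interval in weeks, and the test label pulls the reader the other way.

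The SE might be meant as that of the between-arm difference. In that case the shortfall near no effect would disappear. The wording is against it, because the Overview separates within-group mean changes from the difference between groups and 8.7 uses the former term. The text does not exclude it.

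The 29% figure is a special case. It needs equal SEs and nearly uncorrelated arm means, and it applies where there is little time saving to report. This objection stands, which is why the lower ranges belong beside it. The figures of 7.5 and 10.5 weeks are also illustrative: SAP 6.1.4 expects extra missing data from early termination, and a curved decline makes the bars asymmetric.

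A reader might go further and infer that the bars are 29% too narrow at the planned effect, or that the efficacy conclusions rest on understated error. The documents support neither. They do not fix the shortfall at 45% slowing. The co-primary tests in SAP 8.1 use between-arm contrasts, which carry both arms' error, and SAP 6.1.3 leaves the time analysis outside the testing sequence.

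**Conclusion.** The point holds as a minor one. On the natural reading of 8.7, the bars omit the placebo curve's sampling error and understate the uncertainty of weeks saved. The direction is clear under the conditions examined; the size is conditional. The no-effect figure of about 29%, or 21–27% with equally weighted pooled sites, turns on arm SEs and on an LS-mean weighting that the SAP leaves open. The 45% figure of roughly 7–29% turns on inputs the documents do not supply. The consequence is confined to the time-component tables and figures.

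**What to change.** In SAP 8.7, replace the plus-or-minus-SE mapping with a 95% interval for time saved that carries both arms' error. Two routes are suitable:
- an arm-stratified participant bootstrap that repeats the whole mapping, including the extrapolation rule; or
- inversion of the between-arm comparison: all times t at which the active Week 76 LS mean minus the placebo curve at t lies within 1.96 SEs of zero, with the SE taken from the joint covariance of the LS means.

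The delta method is suitable only when the mapped time is well inside the follow-up range, because of the kink at Week 76.

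Call the result an estimate rather than a test, in 8.7 and in the table and figure titles. If the present bars are kept as well, name the arm and label them: *active mean plus or minus 1 SE; placebo curve treated as fixed*.

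The cost is SAP wording and some programming, with no new data. The downside is wider intervals.

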2.1. Overall Design

The original plans for the study are detailed in the following paragraphs. However, this study was stopped early. The blinding and all other aspects of this study as described below were followed through the termination announcement on November 25, 2024 and thereafter. Learnings from analyses of the sister study, PTI-125-07, were incorporated into this analysis plan.

This is a randomized, double-blind, placebo-controlled, parallel-group study of 76 weeks (19 months) duration in subjects with mild-to-moderate AD. The safety and efficacy of simufilam 50 and 100 mg tablets given twice daily will be evaluated with regard to the slowing of cognitive and

Version 1.0 | 28-Feb-2025 Page 11 of 56

functional decline in AD subjects from 50 to 87 years of age.

In this Phase 3 clinical study, approximately 1083 participants with mild-to-moderate AD (361 per arm) will receive placebo or 50 mg tablets of simufilam or 100 mg tablets of simufilam, twice daily, for 76 weeks. Randomization (1:1:1) will be stratified by low or high mini-mental state exam (MMSE) (16-20 and 21-27).

Study participants 50-87 years of age will be selected for screening based on a diagnosis of AD consistent with Stages 4 or 5 on the Alzheimer's continuum (National Institute on Aging – Alzheimer's Association 2018). Participants must have MMSE \geq 16 and \leq 27, and a Clinical Dementia Rating Global Score (CDR-GS) of 0.5, 1 or 2. Finally, participants must have confirmed positron emission tomography (PET) or fluid biomarker evidence of AD pathophysiology prior to randomization.

Once participants have been satisfactorily screened for study participation, visits to the research clinic will occur on Study Day 1 and at Weeks 4, 16, 28, 40, 52, 64 and 76.

The co-primary endpoints include:

- 1. The 12-item Alzheimer's Disease Assessment Scale Cognitive Subscale (ADAS-Cog12) and
- 2. The Alzheimer's Disease Cooperative Study Activities of Daily Living (ADCS-ADL).

[figure not shown]
Secondary endpoints include the integrated Alzheimer's Disease Rating Scale (iADRS), Neuropsychiatric Inventory (NPI), MMSE, and the Clinical Dementia Rating Sum of Boxes (CDR-SB). A brief questionnaire assessing caregiver burden, the Zarit Burden Interview (ZBI), will be collected as an additional secondary endpoint.

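### The time-saved mapping in SAP 8.7 inverts a placebo curve that is not guaranteed to be one-to-one, so it can give more than one week, or show time saved for an arm that declined more than placebo

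*SAP*

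**What the plan says.** SAP 8.7 describes the co-primary changes as time savings. The active arm's Week 76 mean change is "mapped back to the time point at which the mean change in the placebo arm was equal to the active arm change at Week 76". The interpolator is a cubic spline: "A cubic spline interpolation will be used for precise time mapping between visits". The mean plus and minus one SE are mapped in the same way.

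There is one special case, introduced by "If a time mapping is outside the range spanned by the reference trajectory". Such values are placed on a straight line from (0, 0) to the last visit. The scope is given by "This time component test will be done based on all participants and for the mild and moderate subgroups".

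The knots are the scheduled visits (SAP 2.1): "visits to the research clinic will occur on Study Day 1 and at Weeks 4, 16, 28, 40, 52, 64 and 76". SAP 8.7 sets no monotonicity condition, no rule for several matching weeks and no spline end condition. The results appear as the Time Component Test tables and figures in SAP 13.2 and 13.5, in the ITT set.

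**The concern.** Reading a week off the placebo curve works only if each value of change occurs at one week. Observed visit means can fall back by chance, and a cubic spline can turn between knots even when the visit means rise throughout. Two failures follow from the rule as written.

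- **Ambiguity.** If placebo rises, dips and rises again, a value inside the dip matches three weeks. The reported figure is then whichever root the program returns.
- **Wrong sign.** If placebo peaks before Week 76, an active value between the Week 76 value and the peak is worse than placebo at Week 76 but still inside the range spanned. The straight-line rule does not apply, and the spline returns a week before 76, shown as time saved.

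At stake is a planned table for each co-primary endpoint whose number may be arbitrary, or whose sign may contradict the co-primary difference.

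**Working it through.** **Design figures.** SAP 2.2: "The power calculation assumes a true mean change from baseline for placebo of 6.0 points and a standard deviation of 10.0 points", and the comparison "requires group sizes of 289 to provide 90% power to detect a 45% difference from placebo at 76 weeks". The difference is 0.45 × 6.0 = 2.7 points. Then n = 2 × 10² × (1.960 + 1.282)² / 2.7² = 288.3, rounded up to 289 per arm, with power 0.9007; 289 / 0.80 = 361.25. The SAP's figures of 289 and 361 are reproduced. SAP 8.7 states no figure of its own.

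**Wrong-sign example (invented means, higher is worse).** Placebo changes at Weeks 0, 4, 16, 28, 40, 52, 64, 76: 0, 0.2, 0.9, 1.6, 2.4, 3.1, 3.7, 3.5. Active at Week 76: 3.6, which is 0.1 worse than placebo. Solving spline(t) = 3.6:

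| End condition | Matching weeks | Weeks saved (76 − t) |
|---|---|---|
| Not-a-knot | 61.2 and 74.5 | 14.8 and 1.5 |
| Natural | 60.8 and 73.0 | 15.2 and 3.0 |

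All four answers show time saved, and the unstated end condition changes the result. The SAP's own off-range line would give 76 × 3.6 / 3.5 = 78.2, that is, 2.2 weeks lost.

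**Ambiguity example.** Suppose placebo is 2.2 at Week 28 and 2.0 at Week 40, then keeps declining. Any continuous curve from 0 passes 2.1 before Week 28, between Weeks 28 and 40, and after Week 40. One such series gave Weeks 26.1, 34.7 and 42.7.

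**Frequency.** The documents give no subgroup sizes, subgroup declines or between-visit correlations, so these are assumptions. Setup: linear true decline, SD 10 at Week 76, random slope plus visit-error variance 9 or 16 (Week 64–76 correlation 0.89 or 0.82), natural spline, 20,000 trials per setting. Ranges run over both variances and true effects of 0 and 45%.

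| Per arm, placebo decline | Point estimate ambiguous | Any of mean, ± SE ambiguous |
|---|---|---|
| 289, 6 points (SAP inputs) | 0.01–0.15% | 0.02–0.4% |
| 145, 6 points | 0.1–1.1% | 0.3–3.4% |
| 145, 4 points | 0.6–5.4% | 2–14% |
| 75, 4 points | 2–12% | 8–30% |

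Time saved for an arm worse than placebo occurred in 0.3–1.0% of all trials at 145 per arm and in 1.0–2.2% at 75 per arm, both with a 4-point decline.

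Visit-error variance drives these rates. At SD 8, 150–220 per arm, declines of 3–5 points and variances of 9, 16 and 25, any-of-three ambiguity with a 45% effect ran from 0.5% to 41%. With no effect, wrong sign ran from 0.03% to 4.4%. For all participants, the highest any-of-three rate across the reruns was about 1.4%.

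**The case against.** Time saved is not an objective, an estimand or a step in the testing order of SAP 6.1.3. SAP 8.7 only describes mean changes, and the co-primary difference in the mITT set is reported separately, so a contradictory sign would be visible. That stands, and it limits the point to a descriptive output. A reader might infer that time saved is the headline clinical translation of the result; nothing in the documents says so.

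The frequencies depend on assumed subgroup inputs and on visit noise that no document states. That also stands: they are ranges over assumptions, not predictions. About two-thirds of the any-of-three rate comes from the SE mappings rather than the point estimate.

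Three stronger readings fail:

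- **The spline is never invertible.** It is only not guaranteed to be. With all participants and the SAP's inputs, a unique answer is the normal outcome.
- **More than 76 weeks saved is an error.** An active mean of −0.5 against placebo 6.0 maps to 76 × (−0.5) / 6.0 = −6.3, so 82.3 weeks saved. That follows from a deliberate extrapolation rule and signals improvement over baseline. A cap at 76 would make no change and improvement look alike.
- **The spline must be replaced by an isotonic fit.** Isotonic fits have flat stretches. In the example above, Weeks 64 and 76 pool to (3.7 + 3.5) / 2 = 3.6, and an active 3.6 then matches every week from 64 to 76.

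**Conclusion.** The point holds as a minor specification gap. The rule in SAP 8.7 can return several weeks, and can report time saved for an arm that declined more than placebo; nothing elsewhere in the SAP prevents either. This follows from the text and the worked example, without simulation.

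Its size is modest. For all participants with a 6-point decline, SD 10 and 289 per arm, it arises in roughly 1% of trials or fewer. In assumed smaller or slower-declining subgroups, at least one of the three mapped values is ambiguous in about 3–40% of trials and the sign is wrong in about 0.1–4%; low-noise or faster-declining settings fall below that. SAP 6.1.4 expects more missing data than planned because of the early stop. Fewer late visits would make the late placebo means noisier, and those means drive the wrong-sign case. The co-primary inference is unaffected.

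**What to change.** Keep the spline and the existing off-range extrapolation, and add to SAP 8.7:

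1. If the value being mapped is worse than the observed placebo LS mean change at Week 76 (higher for ADAS-Cog12, lower for ADCS-ADL), always use the existing off-range line, so that no time saved is reported.
2. If the value matches more than one week, report the latest matching week, which is the least time saved.
3. Name the spline end condition.

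In the example, rule 1 gives 2.2 weeks lost instead of 1.5 to 15.2 weeks saved. In the dip example, rule 2 gives Week 42.7, or 33.3 weeks saved.

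The cost is three sentences and a few lines of code, with no new data. Time saved becomes slightly conservative when the placebo curve is not monotone. One limit remains. With the example's placebo means, an active value of 3.45, only 0.05 better than placebo, still maps near Week 59 by linear interpolation (52 + 12 × 0.35 / 0.60). The rules make the answer definite and its sign right, but not smooth, so the placebo trajectory should be shown beside it.
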